10.0 Data and Specimen Banking

10.1 The principal investigator [name],co-investigators [name] and [name], and research assistant [name] will serve as custodians of all research data. As stewards of the research data, these individuals will be responsible and accountable for research data as it

is collected, processed, stored, analyzed, and reported. Every effort will be made to maintain high quality data that will remain protected and kept strictly confidential in accordance with local, state, and federal law; as such, institutional resources REDCap (Research Electronic Data Capture) and NITRO Study Tracker will be used for data entry and monitoring. Once all data collection forms and medical charts have been reviewed, all identifiers will be removed and subject data will be stored and archived in a deidentified manner. The identifiable data will be permanently discarded by permanently deleting the password protected encrypted database with patient identifiers at the earliest opportunity.

- 10.2 Once the data collection forms and medical charts have been reviewed, all identifiers will be removed, and patient data will be stored in a de-identified manner (for the list of data to be stored, please see attached 'stored data' form). Data will be stored in accordance with Northwestern University Information Technology (NUIT) File Sharing Policy using SharePoint and Northwestern file servers, which are available for storing and sharing sensitive research data in order to maintain confidentiality and privacy. Only the study investigators who are on the Authorized Personnel list of the IRB approved protocol will be granted access to the research data.
- 10.3 De-identified data will be stored in accordance with NUIT File Sharing Policy using SharePoint and Northwestern file servers, which are available for storing and sharing sensitive research data in order to maintain confidentiality and privacy. Only the study investigators who are on the Authorized Personnel list of the IRB approved protocol will be granted access to the research data.

11.0 Data and Specimen Management

11.1 Data Analysis Plan: All outcome data will be collected and entered into the computer database before breaking the code and revealing intervention assignment. All analyses will be performed using the intention to treat principle. Descriptive statistics (means, standard deviations, proportions) will be calculated to check for any major differences in the study groups with regard to patient demographics and other baseline characteristics. All univariate comparisons will be unpaired and all tests of significance will be two tailed. For univariate analysis, continuous variables will be compared by Student's t-test. Categorical data will be compared using Chi-square testing or Fisher's Exact Test, depending on sample size. All values will be expressed as the mean + standard error (continuous variables) or as a percentage of the group from which they were derived (categorical variables). A p value of less than 0.05 will be considered statistically significant. An interim analysis of the first 100 patients will be performed by an independent expert physician, and the Havbittle-Peto rule will be used as a guide for stopping the trial if the analysis of the primary outcome demonstrates a significant difference between the group using a p <0.001. The overall type I error rate will be preserved at 0.05.

Page 11 of 23 Revised Template: November 10, 2014

- 11.2 Power Analysis: We based our power analysis on our previous work, literature review, and a review of recent institutional data. During the 12-month period prior to this proposal, the rate of cesarean delivery at NMH was 22.4% for nulliparous women with term singletons pregnancies who received oxytocin prior to delivery and had fetuses in the vertex presentation. For the purpose of the study design, a slightly lower rate was assumed for a population of women delivering at term that excluded women with history of prior uterine surgery and those undergoing induction of labor. A sample-size calculation suggests that, assuming a cesarean delivery rate of 20% in the traditional management LDOR group, 1002 patients (501 patients per group) would be required for this sample to provide 80% power to detect a decrease in the rate of cesarean delivery to 13.4% (one-third decrease) in the HDOR group. Chi-squared test comparing two independent proportions at a two-sided significance level of 0.05 is assumed in the power calculation.
- 11.3 Data Security: A Data Security Plan will be developed to ensure that protected health information and personally identifiable information will be entered, stored, transmitted, analyzed, and reported in a manner that maintains confidentiality. All the members of the study investigative team will be included on the Authorized Personnel list of the IRB approved protocol; only these individuals who are authorized will be granted access to the research data. All members of the study investigative team will be trained and certified by the Collaborative Institutional Training Initiative (CITI) Program. Data integrity and confidentiality will be maintained in several ways. Sources of data include patient records (electronic and paper), patient care providers, and subjects. All data will be collected using standardized data collection forms. Once all data collection forms and medical charts have been reviewed, all data obtained will be entered in a HIPAA compliant into an electronically (passwords and encryption) protected and secure server maintained by NUIT. All identifiers will be removed and patient data will be stored and archived in a de-identified manner. The identifiable data will be permanently discarded by permanently deleting the password protected encrypted database with patient identifiers at the earliest opportunity. Data will be stored in accordance with NUIT File Sharing Policy using SharePoint and Northwestern file servers, which are available for storing and sharing sensitive research data in order to maintain confidentiality and privacy. The data collected and transmitted to the central server is designed to strengthen de-identification and prevent any possibility of linking data to specific subjects. Specifically, subject name, initials, date of birth, date of admission, date of delivery, date of enrollment will be removed from the database at the earliest opportunity. We will organize dataset entries by unique subject study numbers (coinciding with drug treatment code number) in an anonymous manner. No patient specimens will be collected. Only the principal investigator ([name]), co-investigators [name] and Dr.

Page 12 of 23 Revised Template: November 10, 2014

- [name], andresearch assistant [name] ([name]) will have access to data in an identifiable manner before final de-identification.
- 11.4 Quality Control of Collected Data: Data collection forms will be developed, pretested, and used by the investigators and trained clinical staff to gather baseline and outcome data. Investigator meetings will be held on a quarterly basis, including just prior to the initiation of patient enrollment. After initiation of patient enrollment, investigator meetings will be held monthly for the first three months to discuss any questions regarding the protocol, and also as needed thereafter. Data will be extracted from the electronic medical record system, and investigators and clinical staff will remain blinded to group assignment during the data collection process. Every effort will be made to maintain high quality data; as such, institutional resources REDCap and NITRO Study Tracker will be used for data entry and monitoring.
- 11.5 Describe how data and specimens will be handled study-wide:
 - i. Clinical data that is pertinent to the study endpoints will be extracted from the medical record of each subject (see 'data collection' form) and will be recorded on a standard data collection form. Once all data collection forms and medical charts have been reviewed, all identifiers and protected health information will be removed and research data will be stored and archived in a de-identified manner. The identifiable data will be permanently discarded by permanently deleting the password protected encrypted database with patient identifiers at the earliest opportunity.
 - ii. Data will be stored in accordance with Northwestern University Information Technology (NUIT) File Sharing Policy using SharePoint and Northwestern file servers, which are available for storing and sharing sensitive research data in order to maintain confidentiality and privacy. Only the study investigators who are on the Authorized Personnel list of the IRB approved protocol will be granted access to the research data.
 - iii. Research data will be retained and stored for a minimum of three years after the conclusion of the study as per the Northwestern University Policy. However, research data will be kept for as long as deemed necessary to protect any intellectual property resulting from the work. The research data will be stored and archived in a de-identified manner in accordance with NUIT File Sharing Policy.
 - iv. Only the study investigators who are on the Authorized Personnel list of the IRB approved protocol will be granted access to the research data.
 - v. The principal investigator ([name]), the co-investigators [name] and [name], and research assistant ([name]) will serve as custodians of the research data, and will be responsible and accountable for research data as it is collected, processed, stored, analyzed, and reported.

Page 13 of 23 Revised Template: November 10, 2014

vi. Data will be stored in accordance with NUIT File Sharing Policy using SharePoint and Northwestern file servers, which are available for storing and sharing sensitive research data in order to maintain confidentiality and privacy.

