3.2 Criteria

- *i.* Inclusion criteria:
 - Able to give informed written consent
 - o Age ≥18 years
 - Nulliparous
 - Pregnant with a singleton gestation that is equal to or greater than 36 weeks.
 - Diagnosed with at least 6 regular uterine contractions within 60 minutes of observation. In addition, at least one of the following: cervix greater than or equal to 3 cm dilated or 80% effaced OR spontaneous rupture of membranes
 - Subject's attending obstetric physician or midwife has determined that the subject needs administration of oxytocin infusion for labor augmentation. Labor augmentation will be defined as stimulation of uterine contractions when spontaneous contractions have failed to result in progressive cervical dilation or descent of fetus.
- ii. Exclusion criteria:
 - History of prior cesarean section or uterine surgery
 - Fetus in non-cephalic presentation

Page 5 of 23 Revised Template: November 10, 2014

- Subject undergoing labor induction (i.e. receipt of cervical ripening with intracervical foley balloon placement or prostaglandins)
- Non-English speaking

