8.0 Study Endpoints

- 8.1 Study Endpoints
 - i. Primary study endpoint:
 - The incidence of cesarean delivery
 - ii. Secondary study endpoints:
 - Measures of maternal morbidity
 - a. Length of labor duration (defined as the number of hours from admission to labor and delivery to delivery of neonate)
 - b. Incidence of postpartum hemorrhage (defined as an estimated blood loss greater than 500 mL for vaginal delivery or greater than 1000 mL for cesarean delivery)
 - c. Incidence of intrapartum chorioamnionitis (defined as fever great than 100.4° Fahrenheit in the intrapartum period with the initiation of a therapeutic antibiotic regimen in the intrapartum period)
 - d. Incidence of postpartum endometritis (defined as fever greater than 100.4° Fahrenheit in the postpartum period with the initiation of a therapeutic antibiotic regimen in the postpartum period)

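### The primary cesarean comparison is valid and has its stated power, but as an unadjusted test it leaves collected baseline data unused; a prespecified adjusted analysis would add some power with no extra women

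*Combined protocol and SAP*

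**What the plan says.** The primary endpoint in section 8.1 is binary: "The incidence of cesarean delivery". For outcomes of this kind, section 11.1 states, within its account of univariate analysis: "Categorical data will be compared using Chi-square testing or Fisher's Exact Test, depending on sample size". Section 11.2 uses the same test for sizing: "Chi-squared test comparing two independent proportions at a two-sided significance level of 0.05 is assumed in the power calculation".

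The documents contain no adjusted model, covariate list or adjusted sensitivity analysis. Section 9.1 describes blocked allocation with no stratification factors.

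Section 11.4 provides for baseline as well as outcome data to be gathered. In section 11.1 their only role is a descriptive check for "any major differences in the study groups with regard to patient demographics and other baseline characteristics". The plan does not define a major difference or say what follows if one is seen.

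Section 3.2 sets thresholds for age and gestational age, so both must be known for every woman. On labor status it asks, besides regular contractions, for "at least one of the following: cervix greater than or equal to 3 cm dilated or 80% effaced OR spontaneous rupture of membranes".

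**The concern.** Age, gestational age and the state of labor at entry could each help predict who has a cesarean. If they do, adjusting for them removes outcome variation that has nothing to do with oxytocin dose and corrects chance imbalance in those factors. The crude test does neither, and unstratified allocation does not balance them by design.

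Two things are at stake. One is precision: the sample size only just meets its 80% target and includes no allowance for loss, so any efficiency gain is useful. The other is prespecification. If the baseline table shows a difference that someone considers major, the plan has no rule, and an adjustment chosen then would be chosen with the groups in view. Fixing the adjustment while blinded removes that possibility.

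**Working it through.** **Inputs from section 11.2.** The control rate comes from "assuming a cesarean delivery rate of 20% in the traditional management LDOR group", the target from "80% power to detect a decrease in the rate of cesarean delivery to 13.4% (one-third decrease) in the HDOR group", and the size from "1002 patients (501 patients per group) would be required". The test is a two-sided chi-square at 0.05.

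**1. Reproduce the stated size.** With p1 = 0.20, p2 = 0.134, difference d = 0.066 and mean rate 0.167:

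- A = √(2 × 0.167 × 0.833) = 0.5275
- B = √(0.20 × 0.80 + 0.134 × 0.866) = 0.5254
- n per group = [(1.960 × A + 0.8416 × B) / d]² = 500.1, rounded up to 501, or 1,002 in total. This matches the plan exactly.

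**2. Power of the planned test.** Power = Φ[(d√n − 1.960 × A) / B]. At n = 501 this is Φ(0.844) = 80.07%. The plan delivers the power it states.

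**3. Power with adjustment.** Let R2 be the share of outcome variance within a group that the baseline covariates explain. As an approximation, adjustment acts like an effective group size of 501 / (1 − R2), put into the formula of step 2. The documents give no R2, so a range is assumed:

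| Assumed R2 | Effective n per group | Power | Equivalent unadjusted total |
|---|---|---|---|
| 0 | 501 | 80.1% | 1,002 |
| 1% | 506.1 | 80.5% | about 1,012 |
| 3% | 516.5 | 81.3% | about 1,033 |
| 5% | 527.4 | 82.0% | about 1,055 |
| 10% | 556.7 | 84.0% | about 1,113 |
| 15% | 589.4 | 86.0% | about 1,179 |

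**4. Check by simulation.** Each scenario used 6,000 trials of 501 per group, one standardized baseline score, and overall rates held at 20% and 13.4%. The standardized risk difference was compared with the crude chi-square:

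| R2 (AUC of the score) | Adjusted | Crude |
|---|---|---|
| 0 (0.50) | 81.1% | 80.8% |
| about 1% (0.58) | 80.7% | 79.9% |
| about 3% (0.63) | 81.8% | 80.0% |
| about 6% (0.68) | 83.1% | 80.9% |
| about 12% (0.74) | 85.5% | 80.0% |
| about 19% (0.79) | 86.9% | 79.9% |

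The simulation error of each figure is about √(0.8 × 0.2 / 6,000) = 0.5 points. A covariate with no predictive value shows an apparent gain of 0.3 points, so the smallest gains should not be read closely. With no true difference, the rejection rate was 4.6% to 5.0% for the crude test and 4.8% to 4.9% for the adjusted one. The two methods agree: about 1 to 2 points for weak or modest predictors, and about 5 to 7 only for strong ones.

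**5. Which covariates can be relied on.** Age and gestational age follow from eligibility. The cervical and membrane criteria in section 3.2 are alternatives, so a woman may enter on ruptured membranes without meeting any dilation or effacement threshold. The data collection form is an attachment that is not shown. Under sections 7.1 and 19.1, randomization comes after consent, when oxytocin is to be started, so a triage examination may be some time out of date by then.

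**The case against.** The strongest reply is that nothing here is broken. The chi-square is valid, it is the test on which the trial was sized, and with no stratification factors nothing has to be carried into a model. With about 500 women per group, large chance imbalance is unlikely, and the error rate of the test already allows for it. The primary outcome is mode of delivery in the same hospital stay, so little loss is to be expected. The R2 is assumed, and a population limited to nulliparous, singleton, cephalic, non-induced labors at 36 weeks or more may have a narrow prognostic spread. Section 7.1 reports 839 women enrolled by July 2019, which is late to replace a primary test.

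Most of this stands as a limit on size. It rules out two stronger readings that a reader might draw:

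- **That the trial is underpowered or its test wrong.** The stated sample size reproduces exactly.
- **That a full set of labor characteristics is already recorded for every woman and merely ignored.** The entry criteria are alternatives, the form is not visible, and the last cervical value before randomization may not be the one taken at triage. Only age and gestational age are assured, and these are not labor characteristics.

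The reply does not remove the point. An earlier cervical examination still precedes randomization and is a legitimate covariate. Availability can be checked while blinded. Section 11.1 requires all outcome data to be entered before the code is broken, so as of this version the change could still be made without knowledge of the results.

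**Conclusion.** The point holds as a recommended improvement at almost no cost, not as an error. The crude comparison keeps its stated 80.1% power. Prespecified adjustment would be expected to bring it to about 80.5% to 82.0% if baseline factors explain 1% to 5% of the outcome variance, and to 84% to 86% only if they explain 10% to 15%.

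These figures rest on the rates in section 11.2, outcomes for all 1,002 women, and an R2 that the documents do not supply. If only age and gestational age prove usable, the low end is the prudent expectation. The gain in prespecification, a fixed adjustment that does not depend on what the baseline table shows, does not depend on R2.

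**What to change.** Before the code is broken, add one paragraph to section 11.1 that:

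- makes the primary analysis a logistic regression of cesarean delivery on treatment group and baseline covariates, standardized to a marginal risk difference and risk ratio with 95% confidence intervals. Standardizing matters because an adjusted odds ratio is a conditional effect, whereas the trial was sized on a difference in overall rates;
- names maternal age and gestational age as covariates;
- adds the last cervical dilation before randomization, membrane status and BMI, each only if a blinded review confirms that it is on the form with few missing values;
- fixes a simple rule for missing baseline values, for example filling in the overall mean or most common category from the pooled blinded data;
- keeps the crude chi-square as a supporting analysis.

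The cost is that paragraph, the blinded review of the form and minor programming; no extra women are needed. If the team does not wish to move the primary test at this stage, prespecifying the adjusted analysis as a sensitivity analysis would still settle how baseline differences are handled, but the primary test would not gain the added power.

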- ii. Statistical tests will be used to analyze the safety data to determine whether harm is occurring. All univariate comparisons will be unpaired and all tests of significance will be two tailed. For univariate analysis, continuous variables will be compared by Student's t-test. Categorical data will be compared using Chi-square testing or Fisher's Exact Test, depending on sample size. All values will be expressed as the mean ± standard error (continuous variables) or as a percentage of the group from which they were derived (categorical variables). A *p* value of less than 0.05 will be considered statistically significant. The *p* value will not be adjusted for the interim analysis given its early timing.

Page 14 of 23 Revised Template: November 10, 2014

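### Section 11.1 says overall type I error is preserved at 0.05, but no final level below 0.05 is given, so as written it is slightly exceeded

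*Combined protocol and SAP*

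**What the plan says.** Section 11.1 (Data Analysis Plan) makes four statements that bear on the primary test:

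- On sidedness: "All univariate comparisons will be unpaired and all tests of significance will be two tailed".
- On the level: "A p value of less than 0.05 will be considered statistically significant".
- On the interim: "An interim analysis of the first 100 patients will be performed by an independent expert physician". The Haybittle-Peto rule serves as a guide for "stopping the trial if the analysis of the primary outcome demonstrates a significant difference between the group using a p <0.001".
- On the result: "The overall type I error rate will be preserved at 0.05".

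Section 11.2 (repeated in section 23.0) bases 1002 patients on a chi-squared test at a two-sided 0.05, with no allowance for the interim.

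Section 12.1 ii opens on the analysis of safety data, repeats the p<0.05 level, and adds that the p "value will not be adjusted for the interim analysis given its early timing". Section 12.1 i describes the look after 100 patients as covering safety or efficacy.

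**The concern.** A plan can state that overall error is held at 0.05, or it can decline to adjust for an early look and accept a slightly larger error. It cannot strictly do both. Section 11.1 does the first and names no final level that would deliver it. Section 12.1 ii does the second.

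This is the decision rule for the primary endpoint. A final p between about 0.049 and 0.05 would be declared significant under a control claim that the design does not quite meet. The choice of threshold would then be open to argument after the result is known.

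The scope of the sentence in 12.1 ii adds to the uncertainty. It stands among safety analyses, but the section also gives the look an efficacy purpose. In addition, the primary safety endpoint in section 8.2 (cesarean for nonreassuring fetal status) is a subset of the primary outcome in section 8.1 (all cesareans). The text does not say outright which level can stop the trial on which endpoint.

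**Working it through.** **Inputs.** Interim at 100 patients, p<0.001; final p<0.05; two-sided tests (section 11.1). Total 1002, 501 per group, 20% versus 13.4%, chi-squared test (section 11.2). Equal allocation (section 9.1). Assumed: the 100 interim patients split 50/50.

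**1. The plan's sample size.** The pooled chi-squared formula without continuity correction is

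n = [z(α/2)·√(2p̄(1−p̄)) + z(β)·√(p1(1−p1)+p2(1−p2))]² / (p1−p2)²

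With p̄ = 0.167 the two roots are 0.5275 and 0.5254. So n = (1.960×0.5275 + 0.8416×0.5254)² / 0.066² = 500.1, rounded up to 501 per group, or 1002. The plan's figure reproduces at the full 0.05.

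**2. Overall error as written, normal approximation.** Under the null, the interim and final statistics are bivariate normal with correlation √(100/1002) = 0.316. The critical values are 3.291 (p<0.001) and 1.960 (p<0.05).

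Overall error = 1 − P(|Z1|<3.291, |Z2|<1.960) = 0.0508

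The simple upper bound is 0.001 + 0.05 = 0.051. With a final size of 839 (the enrollment that section 7.1 reports for July 2019) in place of 1002, the result is still 0.0508.

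**3. Overall error as written, exact.** The two-stage chi-squared test (50+50, then 501+501) was enumerated with binomial probabilities at a common cesarean rate.

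| Common rate | Spent at interim | Overall, final 0.05 | Overall, final 0.049 |
|---|---|---|---|
| 13.4% | 0.0005 | 0.0503 | 0.0492 |
| 16.7% | 0.0006 | 0.0501 | 0.0498 |
| 20% | 0.0008 | 0.0505 | 0.0496 |
| 22.4% | 0.0008 | 0.0505 | 0.0497 |

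The exact excess is below the asymptotic one because the discrete interim test spends less than 0.001. Section 11.1 also permits Fisher's exact test depending on sample size. With Fisher at the interim and chi-squared at 0.05 at the end, the overall values at the four rates are 0.0502, 0.0500, 0.0502 and 0.0502.

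**4. Final level that makes the claim true.** Solving step 2 for an overall 0.05 gives a final level of 0.0492. The simple split, 0.05 − 0.001 = 0.049, gives 0.0498 by the normal approximation, and the last column of the table stays below 0.05 throughout.

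**5. Cost in power at 501 per group.**

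Power = Φ{[0.066×√501 − z(α/2)×0.5275] / 0.5254}

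- At 0.05 (z = 1.960): 80.07%
- At 0.0492 (z = 1.967): 79.87%
- At 0.049 (z = 1.969): 79.83%

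Holding a full 80% would need 503 per group at 0.0492, or 504 at 0.049.

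**The case against.** The strongest reply is that nothing material is wrong. A stopping guide of p<0.001 at one very early look, with a nominal 0.05 at the end, is the usual Haybittle-Peto layout. The plan says that it leaves the level alone and gives the reason. The value 0.0508 rounds to 0.05, the exact excess is about 0.0001 to 0.0005, and with Fisher's test at the interim it nearly vanishes. The p<0.001 rule is also only a guide: if the trial runs to the end regardless and only the final test counts, the interim adds no error. Finally, the preservation claim could be read as an unstated commitment to lower the final level, in which case 0.05 holds.

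Most of this stands, and it sets the severity. It does not remove the point. The commitment to a lower final level needs a number that the documents do not contain, and it sits badly with the stated p<0.05 and with a power calculation at the full 0.05. If that was the intention, the remedy is still to write the level down.

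A reader might infer two stronger readings, and the documents support neither.

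- That p<0.001 and p<0.05 contradict each other, or give two thresholds for the same test at the interim. They do not: section 11.1 assigns p<0.001 to the primary outcome at the interim, while the p<0.05 in 12.1 ii is introduced for safety data and is not called a stopping boundary.
- That the primary outcome is tested at p<0.05 at both looks, which would put the overall error near 0.095. That requires overriding the explicit p<0.001 in section 11.1, so the figure does not describe this design.

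**Conclusion.** The point holds, at minor severity. As written, the overall two-sided error for the primary outcome is slightly above the 0.05 that section 11.1 says is preserved: 0.0508 asymptotically, about 0.0501 to 0.0505 by exact chi-squared enumeration, and never more than 0.051 by the simple bound. The inconsistency is between the preservation claim and the refusal to adjust.

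The figures assume that the interim rule is followed as a stopping rule, that the 100 patients split evenly, that the final test is an uncorrected chi-squared, and that the null cesarean rate lies between 13.4% and 22.4%. Only a final p between about 0.049 and 0.05 would be affected.

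**What to change.** In section 11.1, state that the primary outcome is tested at the final analysis at two-sided p<0.049, with the interim at p<0.001, for an overall error of at most 0.05. If the final 0.05 is kept, replace the preservation claim with a statement that overall error is approximately 0.05 (at most 0.051).

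In section 12.1 ii, limit the no-adjustment sentence to the safety comparisons, and state that p<0.001 is the only stopping threshold for the primary outcome.

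The cost is a few sentences, no extra patients, and about 0.2 percentage points of power under the first option (none under the second). Section 7.1 reports 839 enrolled with the primary analyses still to come, and section 11.1 breaks the code only after all outcome data are entered. On the documents, the change can therefore be made before unblinding.
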